## **7 STUDY INTERVENTION DISCONTINUATION AND PARTICIPANT DISCONTINUATION/WITHDRAWAL**

### **7.1 DISCONTINUATION OF STUDY INTERVENTION**

Study product administration for any given subject may be stopped for SAEs, clinically significant adverse events, severe laboratory abnormalities, or any other medical conditions that indicate to the Investigator that continued dosing is not in the best interest of the patient.

See section 6.1.2.3 for information on dosing modifications or discontinuation rules based on laboratory abnormalities or other adverse events.

Subjects who have the study product stopped for a safety related issues will not continue with dosing. In addition, subjects who have an allergic reaction that is temporally associated with study product administration and the PI believes it to be related to study product will not receive any more study product.

In addition, a subject in this clinical study may discontinue study drug at their request for any reason. Every effort should be made to encourage subjects to remain in the study for the duration of their planned outcome assessments. Subjects should be educated on the continued scientific importance of their data, even if they discontinue study drug.

Unless the subject withdraws consent, those who discontinue study drug early will remain in the study. The reason for subject discontinuation of study drug should be documented in the CRF.

Discontinuation from the study drug does not mean discontinuation from the study, and remaining study procedures should be completed as indicated by the study protocol. If a clinically significant finding is identified (including, but not limited to changes from baseline) after enrollment, the investigator or qualified designee will determine if any change in participant management is needed. Any new clinically relevant finding will be reported as an adverse event (AE).

The data to be collected at the time of study intervention discontinuation will include the following:

- Reason for discontinuation
- Date of last study drug administration
- Any adverse event
- Patients will be followed for clinical data required for the duration of the study

Participants are free to withdraw from participation in the study at any time upon request.

An investigator may discontinue a participant from study drug for the following reasons:

- Disease progression which requires discontinuation of the study intervention
- If any clinical adverse event (AE), laboratory abnormality, or other medical condition or situation occurs such that continued participation in the study would not be in the best interest of the participant
- Positive pregnancy test
- Participant unable to receive study drug
- Lost to Follow Up

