##### **6.1.2.3 Dose Modifications**

Adverse Reaction	Recommended action
Hypertension	

*Abbreviated Title: Fostamatinib for COVID*

*Version Date: 09/17/2020*

Stage 1: systolic between 130-139 or diastolic between 80-89 mmHg	Initiate or increase antihypertensive medication for patients with increased risk of cardiovascular risk, and adjust as needed. No dose modification to study drug required.
Stage 2: systolic at least 140 or diastolic at least 90 mmHg	Initiate or increase antihypertensive medication and adjust as needed until BP control. No dose modification to study drug required.
Hypertensive crisis: systolic over 180 and or diastolic over 120 mmHg	Discontinue study drug until blood pressure is below systolic blood pressure of 160 and diastolic less than 100 mmHg. When restarting study drug dose should be reduced to 100 mg twice daily or matching placebo for the remainder of the study
Hepatotoxicity	
Increase in AST/ALT by x3 from level at the time of enrollment	Stop study drug and recheck liver function tests the next day. May restart when AST/ALT have returned to less than 3x baseline. When restarting study drug dose should be reduced to 100 mg twice daily or matching placebo for the remainder of the study*
Increase in AST/ALT to 3X ULN and total BL (bilirubin) greater than 2 x upper limit of normal (ULN)	Stop fostamatinib and recheck liver function tests the next day. May restart when AST/ALT have returned to less than 3x ULN and total BL has returned to less than 2x upper ULN. When restarting study drug dose should be reduced to 100 mg twice daily or matching placebo for the remainder of the study*
Elevated unconjugated (indirect) BL in absence of other LFT abnormalities	Continue study drug with frequent monitoring since isolated increase in unconjugated (indirect) bilirubin may be due to UGT1A1 inhibition
Diarrhea	
Diarrhea	Manage diarrhea using supportive measures (e.g., dietary changes, hydration and/or

	antidiarrheal medication) early after the onset until symptoms resolve.  If symptoms become severe (grade 3) or above), temporarily stop study until symptoms resolve to mild (grade 1). When restarting study drug dose should be reduced to 100 mg twice daily or matching placebo for the remainder of the study
Neutropenia	

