Neutropenia	If absolute neutrophil count decreases (ANC less than $1.0 \times 10^9/L$ ) discontinue fostamatinib. When ANC returns to above $1.0 \times 10^9/L$ , restart study drug. When restarting study drug dose should be reduced to 100 mg twice daily or matching placebo for the remainder of the study

\*Parameters and laboratory abnormalities must resolve within 3 days to restart the study drug.

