#### **9.3.4 Safety Analyses**

The planned analyses will also include descriptive statistics on the incidence and severity of adverse events. The proportions of serious adverse events (SAEs) will be summarized using sample proportions and confidence intervals for binomial distributions. Safety will be summarized using descriptive statistics to assess the difference between the two study arms. Summaries will be produced for all adverse events (AEs), related AEs (those considered by the Investigator as related to study treatment), SAEs, AEs leading to treatment discontinuation, and AEs Grade  $\geq 3$  in severity. Individual subject listings will be provided for any deaths, SAEs, AEs leading to interruption and AEs leading to treatment discontinuation for the fostamatinib arm compared to the placebo arm.

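### Section 7.1 bars further dosing after a safety stop, the dose table in 6.1.2.3 restarts study drug after five kinds of safety stop, and no text says which governs

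*Combined protocol and SAP*

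**What the plan says.** Section 7.1 (Discontinuation of Study Intervention) opens by allowing study product to be stopped for SAEs, clinically significant adverse events, severe laboratory abnormalities, or other conditions that in the investigator's view make further dosing unwise. It then points to the dose table: "See section 6.1.2.3 for information on dosing modifications or discontinuation rules based on laboratory abnormalities or other adverse events". The next paragraph begins: "Subjects who have the study product stopped for a safety related issues will not continue with dosing".

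The table in 6.1.2.3 (Dose Modifications) provides for restarts. After hypertensive crisis the instruction is "Discontinue study drug until blood pressure is below systolic blood pressure of 160 and diastolic less than 100 mmHg". After a threefold rise in AST/ALT from the enrollment level, "May restart when AST/ALT have returned to less than 3x baseline". After AST/ALT at three times the upper limit of normal (ULN) with raised bilirubin, "May restart when AST/ALT have returned to less than 3x ULN and total BL has returned to less than 2x upper ULN". For severe diarrhea, "temporarily stop study until symptoms resolve to mild (grade 1)". The neutropenia row also ends in a restart once the count recovers. All five rows carry the same instruction on the restart dose: "When restarting study drug dose should be reduced to 100 mg twice daily or matching placebo for the remainder of the study".

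Section 9.3.4 (Safety Analyses) summarizes events leading to treatment discontinuation and calls for individual listings that separate "AEs leading to interruption and AEs leading to treatment discontinuation".

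**The concern.** All five stops in the table are made for safety reasons. On its plain wording, the sentence in 7.1 covers them and forbids the restarts that the table describes. Two things are at stake.

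The first is a patient-safety instruction. Whether a patient is given study drug again after a liver, neutrophil, blood-pressure or bowel event should not depend on which section a site reads. The trial is multicenter, so two sites could treat the same situation differently, each with text to support it.

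The second is classification. Section 9.3.4 needs a boundary between interruption and discontinuation, and the protocol does not define one. An event classed as a discontinuation enters both a summary and a listing. An event classed as an interruption enters only a listing.

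**Working it through.** The plan gives no figure to reproduce: the sample size in 9.1 is set by feasibility and this point does not depend on it. The check is a comparison of texts.

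**Step 1. Count the table rows that stop drug, and those that restart it.**

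| Row in 6.1.2.3 | Verb for the stop | Restart provided? | Time limit for restart |
|---|---|---|---|
| Hypertension stage 1 | no stop | – | – |
| Hypertension stage 2 | no stop | – | – |
| Hypertensive crisis | discontinue (until) | yes | none |
| AST/ALT threefold from enrollment | stop | yes | 3 days |
| AST/ALT 3 × ULN with bilirubin > 2 × ULN | stop | yes | 3 days |
| Isolated indirect bilirubin | no stop | – | – |
| Diarrhea, grade 3 or above | temporarily stop | yes | none |
| Neutropenia | discontinue | yes | none |

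Of 8 rows, 3 do not stop drug and 8 − 3 = 5 do. All 5 provide for a restart. Read literally, 7.1 therefore cancels every restart provision in the table.

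**Step 2. Ask whether 7.1 exempts the table.** The pointer to 6.1.2.3 comes just before the unconditional sentence and says only where information is found. The sentence itself has no wording that limits it to permanent stops or to events outside the table. The triggers that open 7.1 (SAEs, significant adverse events, severe laboratory abnormalities) are the same kind of event as the table rows, so 7.1 cannot be confined to other events by subject matter. The table's column heading presents its actions as recommended, whereas 7.1 is worded as mandatory. A careful site could therefore take 7.1 as controlling.

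**Step 3. Ask whether the vocabulary separates hold from permanent stop.** It does not do so consistently. *Discontinue* is the title word of 7.1, yet it is also the verb in two rows that restart. The 3-day limit separates the two kinds of stop for the liver rows, which alone carry the asterisk. The other three rows have no such limit.

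**Step 4. Follow the classification through.** Section 7.1 lists data to collect when the intervention is discontinued, including the reason and the date of the last dose. It does not say whether a stop followed by a restart triggers that list. Section 9.3.4 uses both categories without defining either.

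**Step 5. Check the primary analysis.** The primary endpoint is the incidence of SAEs through day 29, in all randomized patients who received any study drug or placebo (9.2.2), compared by Fisher's exact test (9.3.2). None of these elements refers to whether dosing was interrupted, discontinued or resumed.

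**The case against.** The strongest reply is that the intended reading can largely be inferred, and most of the evidence for it is sound.

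- Section 6.1.2 also sends dose modifications for adverse reactions to 6.1.2.3.
- Section 6.2.2 supplies 100 mg tablets and matching 100 mg placebo. All patients start at 150 mg, and the only use of 100 mg in the trial's dosing is the restart in the table. If 7.1 overrode the table, that supply would have no use.
- Section 9.3.4 has an interruption category, so the analysis section expects temporary stops.
- The diarrhea and hypertensive crisis rows read plainly as holds.
- In 7.1 the disputed sentence is followed by a permanent bar for allergic reactions. This fits a reading in which the whole paragraph concerns permanent stops.
- Dose administration, pill counts, the reason for discontinuation and the last-dose date are recorded (6.4, 7.1), so actual interruptions could largely be identified afterwards.

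This lowers the severity. It does not remove the conflict: a rule on giving a drug again after a safety stop should be stated, not deduced from the tablet supply.

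A reader might also infer that the primary safety comparison is compromised. The documents do not support that. The endpoint, its population and its test are the same under either reading. Study drug is blinded (6.3.2) and randomization is stratified by site (6.3.1), so a site's reading applies to both of its arms. What can vary is the amount of drug received after a stop.

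**Conclusion.** The contradiction holds and should be fixed. Section 7.1 and five rows of 6.1.2.3 give opposite instructions on dosing after a safety stop, and no text ranks them. The consequences are an unclear re-exposure rule and an undefined boundary between two reporting categories in 9.3.4. That the text permits sites to differ follows from the wording; that they would differ is an inference.

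The size is best stated as five rows, which are all the rows that stop drug. A reader might go further and apply the rates in 2.3.1 to about 30 fostamatinib patients (60 ÷ 2). That gives 0.09 × 30 = 2.7 if the events overlap fully, and (0.09 + 0.06 + 0.01 + 0.01) × 30 = 5.1 if they do not overlap. The documents do not support that count, for four reasons:

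1. The dominant 9% is for AST/ALT above 3 × ULN, which alone is not a trigger. The triggers are a threefold rise from enrollment, or 3 × ULN with bilirubin above 2 × ULN. AST/ALT up to 5 × ULN can be allowed at entry (5.2). A patient enrolled at 4 × ULN would reach the first trigger at 3 × 4 = 12 × ULN; one enrolled at 0.5 × ULN would reach it at 3 × 0.5 = 1.5 × ULN. So 9% is neither a lower nor an upper bound.
2. The 6% for neutropenia comes with no neutrophil threshold, whereas the table uses 1.0 × 10⁹/L.
3. The rates come from other diseases, with no exposure period given; dosing here lasts 14 days.
4. Meeting a stop trigger is not the same as qualifying for a restart, which also requires recovery, within 3 days for the liver rows.

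The verdict does not depend on any event rate.

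**What to change.** The passages must be reconciled. Section 7.1 should state which safety stops are permanent and which are temporary holds governed by 6.1.2.3. One term should be used for each kind of stop in 6.1.2.3, 7.1 and 9.3.4, so that *discontinue* is not used for a stop that may be followed by a restart. Section 7.1 should also say whether a hold triggers its list of data collected at discontinuation. Which rule applies to which event is for the clinical team to decide.

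The cost is protocol wording only. No additional patients, visits or data are needed, and the primary analysis does not change.

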## **7.2 PARTICIPANT DISCONTINUATION/WITHDRAWAL FROM THE STUDY**

Participants are free to withdraw from participation in the study at any time upon request.

Subjects who withdraw from this study or are lost to follow-up after signing the informed consent form and administration of the study product, will not be replaced. The reason for subject withdrawal from the study will be recorded on the appropriate CRF.

## **7.3 LOST TO FOLLOW-UP**

A participant will be considered lost to follow-up if he or she fails to return for a scheduled visit and is unable to be contacted by the study site staff.

The following actions must be taken to maximize study subject retention and prevent missing data if a participant fails to return to the clinic for a required study visit:

- The site will attempt to contact the participant and reschedule the missed visit within 2 days of the visit and counsel the participant on the importance of maintaining the assigned visit schedule and ascertain if the participant wishes to and/or should continue in the study.
- Before a participant is deemed lost to follow-up, the investigator or designee will make every effort to regain contact with the participant (where possible, 3 telephone calls). These contact attempts should be documented in the participant's medical record or study file.
- Should the participant continue to be unreachable, the clinical team will try to ascertain vital status through vital record search; and the participant will be considered to have withdrawn from the study with a primary reason of lost to follow-up.

## **8 STUDY ASSESSMENTS AND PROCEDURES**

### **8.1 SCREENING PROCEDURES**

#### **8.1.1 Screening activities performed prior to obtaining informed consent**

Minimal risk activities that may be performed before the subject has signed a consent include the following:

- Review of existing medical records to include H&P, laboratory studies, etc.
- Review of existing MRI, x-ray, or CT images.
- Review of SARS CoV-2 test results.

*Abbreviated Title: Fostamatinib for COVID*

*Version Date: 09/17/2020*

8.1.2 Screening activities performed after a consent for screening has been signed

The following activities will be performed only after the subject has signed the consent this study.

- Physical examination
- Pregnancy test (for female subjects of childbearing age)
- Clinical labs (CBC, liver enzymes panel, chemistry panel), if not available
- X-ray, if not available

The overall eligibility of the subject to receive the study drug will be assessed once all screening values are available and completion of an eligibility checklist.

## **8.2 EFFICACY ASSESSMENTS**

For all baseline assessments and follow-up visits, refer to the Schedule of Assessments (SOA) for procedure to be done, and details below for each assessment.

Inpatient assessments will be done at the initial site of patient enrollment (NIH Clinical Center or Inova Health Systems.) After patient discharge, all outpatient assessments will be done at NIH Clinical Center either in person or remotely using NIH approved TeleMedicine software and approved NIH TeleMedicine guidance.

The subject's clinical status will be captured on each study day while hospitalized up until and including Day 60. If a subject is discharged prior to Day 15, clinical status is captured on Day 5, 8, 11, 15, 22, 29, and 60 if the subject returns for an in-person clinic visit or by phone or telehealth if an in-person visit is not possible. Clinical status will also be captured on Day 22 during a phone or telehealth visit. Clinical status is defined by secondary outcomes.

### **8.2.1 Clinical Evaluations**

**Physical examination:** A baseline physical examination will be performed prior to initial study product administration on Day 1. The baseline physical examination can be one that is conducted from screening to Day 1. Post-baseline physical examinations will be done only when needed to evaluate possible adverse event(s) (i.e. any new signs or symptoms). No routine physical exam is needed for study visits after Day 1.

**Radiographic or other imaging assessments.** Chest x-ray are to be done at day 1 and repeated as clinically indicated.

### **8.2.2 Biospecimen Evaluations**

Research bloods will be sent from Inova hospitals to the NIH for processing in either the clinical laboratory -or- in a NHLBI research lab.

The amount of blood that may be drawn from subjects for research purposes shall not exceed 10.5 mL/kg or 550 mL, whichever is smaller, over any eight-week period.

*Abbreviated Title: Fostamatinib for COVID*

*Version Date: 09/17/2020*

Test/assay	Volume blood (approx.)	Type of tube	Frequency****	Location of specimen analysis
Routine* 
 
• CBC
 
• BMP
 
• Hepatic
 
	3 mL  4 mL	EDTA tube (lavender)  Lithium Heparin tube (light green)	Baseline (prior to enrollment)  D1-entire hospitalization, D15, D22, D29, D60 if outpatient	Clinical Lab  At participating sites
Research* 
 
• PT
 
• PTT
 
• INR
 
• Fibrinogen
 
• D-dimer
 
• Von Willebrand factor
 
	3 ml x2	Sod Citrate (BLU) x2	D1, 3, 5, 8, 11, 15, 22, 29, 60	NIH Clinical Lab
Research* 
 
• P-selectin
 
• Thrombomodulin
 
	3 ml	Sod Citrate (BLU)	D1, 3, 5, 8, 11, 15, 22, 29, 60	NIH Clinical Lab
Research* 
 
• IL-6
 
	3mL	EDTA (lavender)	D1, 3, 5, 8, 11, 15, 22, 29, 60	NIH Clinical Lab
Research* 
 
• Ferritin
 
• CRP
 
	4 mL	Lithium Heparin tube (light green)	D1, 3, 5, 8, 11, 15, 22, 29, 60	NIH Clinical Lab
Research (exploratory) 
 
• Serum tube
 
	8 mL	Serum Separator Red top tube	D1, 3, 5, 8, 11, 15, 22, 29, 60	NHLBI Research lab ([name])

*Abbreviated Title: Fostamatinib for COVID*

*Version Date: 09/17/2020*

Research (exploratory) 

• Plasma

	2 mL	Sod Citrate (BLU)	D1, 3, 5, 8, 11, 15, 22, 29, 60	NHLBI Research lab ([name])

• PBMC

	9 ml	Sodium Heparin Green top		
Research (exploratory) 

• TEG**

	3mL	Sodium Citrate	D1, 3, 5, 8, 11, 15, 22, 29, 60	NIH Site and Clinical Lab only
Research (exploratory) 

• RNA***

	5mL	Paxgene	D1, 3, 5, 8, 11, 15, 22, 29, 60	NHLBI Research lab ([name])
Research (exploratory) 

• Cell free DNA***

	5mL	Shreck tube	D1, 3, 5, 8, 11, 15, 22, 29, 60	NHLBI Research Lab ([name])
Research (exploratory) 

• SARS-CoV-2 test*****

	OP swab	Oropharyngeal swab	D1, 3, 5, 8, 11, 15, 22, 29, 60	NIH Clinical Center Lab

\*Residual bloods from clinical care can be transferred to the NHLBI research lab for storage.

\*\*TEG (thromboelastography) to be performed at NIH site only.

\*\*\*Only one of either RNA collections via Paxgene tubes or cell free DNA collection via Shreck tubes will be performed at the discretion of the principal investigator a decision that will be made for each individual patient.

\*\*\*\*Day 1 labs should be drawn prior to first study drug administration.

\*\*\*\*\* SARS-CoV-2 testing done for research purposes. This test will not be used for diagnostic purposes..

In addition to the research blood requested above, we will request residual blood from clinical labs for research purposes, as available for research purposes.

### **8.2.3 Correlative Studies for Research Studies**

As an exploratory endpoint, we will study the immune mechanism by which fostamatinib improves outcomes in patients with COVID-19.

1. Characterization of plasma biomarkers of immune activation
2. Measure platelet-leukocyte aggregates

3. Measure leukocyte activation assays
4. Measure plasma cytokine and chemokine levels
5. Evaluate the coagulation cascade
6. Measurement of immune antigen-antibody complexes
7. Measurement of thromboelastography (TEG)
8. Measure biomarkers of endothelial dysfunction
9. Characterize leukocyte extracellular traps
10. SARS-CoV-2 viability via cell culture from oropharyngeal samples
11. Detection of viral antigen blood and oropharyngeal samples

### **8.2.4 Samples for Genetic/Genomic Analysis**

There are no genetic/genomic analyses planned on any of the samples. If a decision is made to perform DNA or RNA sequencing on any of the samples, the protocol will be amended with a GDSP and ICF updated to reflect this.

- 8.2.4.1 Description of how privacy and confidentiality of medical information/biological specimens will be maximized

N/A

- 8.2.4.2 Management of Results

N/A

- 8.2.4.3 Genetic counseling

N/A

## **8.3 SAFETY AND OTHER ASSESSMENTS**

**Physical examination** A targeted physical examination will be performed at baseline prior to initial study product administration on Day 1. The baseline physical examination can be one that is conducted from screening to Day 1. Post-baseline physical examinations will be done only when needed to evaluate possible adverse event(s) (i.e. any new signs or symptoms). No routine physical exam is needed for study visits after Day 1. Targeted physical exam constitutes assessment of vital signs, neurological, cardiac, and pulmonary exam.

